
- CONFIDENTIAL -

V. FLOW CHART AND SCHEDULE OF ASSESSMENTS

Flow Chart

- CONFIDENTIAL -

Table 1: Schedule of Assessment

Visit	Initiation of Screening ¹⁾	Screening Test Period	0 W	4 W	8 W	12 W	16 W	20 W	24 W	28 W	32 W	36 W	40 W	44 W	48 W	52 W	Early Termination	Follow-up ²⁾	Unscheduled Visit	
Visit day	-1 at latest	-28 to -1	1	29	57	85	113	141	169	197	225	253	281	309	337	365	Within 2 days of withdrawal	28 days after Week 52 or early termination visit	-	
Allowable range from specified date				±7	±7	±7	±7	±7	±7	±7	±7	±7	±7	±7	±7	±7	+2	±7	-	
Informed consent	○																			
Inclusion/exclusion criteria	○	○	○																	
Subject registration	○		○			○										○	○	○		
Confirmation of DMARD-IR	○		○																	
Demographics	○	○	○																	
Medical history	○	○	○																	
Height		○																		
Tuberculin test		○																		
Safety																				
Physical examination		○	○	○	○	○	○	○	○	○	○	○	○	○	○	○	○	○	○	▲
Body weight		○				○				○			○			○	○	○	○	▲
Vital signs		○	○	○	○	○	○	○	○	○	○	○	○	○	○	○	○	○	○	▲
Hepatitis examination		○																		▲
Hematology ³⁾		○	○	○	○	○	○	○	○	○	○	○	○	○	○	○	○	○	○	▲
Biochemistry ³⁾		○	○	○	○	○	○	○	○	○	○	○	○	○	○	○	○	○	○	▲
Urinalysis ³⁾		○	○	○	○	○	○	○	○	○	○	○	○	○	○	○	○	○	○	▲
Fasting lipid profile test			○			○		○		○			○			○	○	○	○	▲
Chest radiography		○								○						○	▲			▲
12-lead ECG		○								○						○	○			▲
Central ECG ⁴⁾			○	○ ⁶⁾																
Pregnancy test ⁵⁾		○	○	○	○	○	○	○	○	○	○	○	○	○	○	○	○	○	○	▲

- CONFIDENTIAL -

Visit	Initiation of Screening ¹⁾	Screening Test Period	0 W	4 W	8 W	12 W	16 W	20 W	24 W	28 W	32 W	36 W	40 W	44 W	48 W	52 W	Early Termination	Follow-up ²⁾	Unscheduled Visit		
Visit day	-1 at latest	-28 to -1	1	29	57	85	113	141	169	197	225	253	281	309	337	365	Within 2 days of withdrawal	28 days after Week 52 or early termination visit	-		
Allowable range from specified date				±7	±7	±7	±7	±7	±7	±7	±7	±7	±7	±7	±7	±7	+2	±7	-		
Adverse events			○	○	○	○	○	○	○	○	○	○	○	○	○	○	○	○	○	▲	
Efficacy																					
CRP and ESR		○ (CRP only)	○	○	○	○	○	○	○	○	○	○	○	○	○	○	○	○	○	○	▲
TJC/SJC (68/66 joints)		○	○	○	○	○	○	○	○	○	○	○	○	○	○	○	○	○	○	○	▲
PGA (VAS), SGA (VAS), and subject's assessment of pain (VAS)			○	○	○	○	○	○	○	○	○	○	○	○	○	○	○	○	○	○	▲
SF-36 v2 [®]			○	○	○	○				○						○	○	○	○	▲	
WPAI			○	○	○	○				○						○	○	○	○	▲	
HAQ-DI			○	○	○	○	○	○	○	○	○	○	○	○	○	○	○	○	○	○	▲
PK/PD																				▲	
Blood sampling for trough concentration ⁴⁾			○	○	○	○				○						○	○				

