Blood sampling for post-dose drug concentration ⁴⁾				○																	
Blood sampling for PD (biomarkers)			○	○	○	○				○						○	○	○	○	▲	
Blood sampling for PD (lymphocyte subset)			○	○	○	○				○						○	○	○	○	▲	
Informed consent for PGx research (relevant sites only) ⁴⁾			○																		
Blood sampling for PGx (relevant sites only) ⁴⁾			○																		

- CONFIDENTIAL -

Visit	Initiation of Screening ¹⁾	Screening Test Period	0 W	4 W	8 W	12 W	16 W	20 W	24 W	28 W	32 W	36 W	40 W	44 W	48 W	52 W	Early Termination	Follow-up ²⁾	Unscheduled Visit
Visit day	-1 at latest	-28 to -1	1	29	57	85	113	141	169	197	225	253	281	309	337	365	Within 2 days of withdrawal	28 days after Week 52 or early termination visit	-
Allowable range from specified date				±7	±7	±7	±7	±7	±7	±7	±7	±7	±7	±7	±7	±7	+2	±7	-
Study drug/reference drug																			
Confirmation of remaining unused drugs				○	○	○	○	○	○	○	○	○	○	○	○	○	○		
Prescription			○	○	○	○	○	○	○	○	○	○	○	○	○				

The symbol “○” designates mandatory items, whereas the symbol “▲” denotes the optional items to be investigated on the basis of the clinical judgment of the investigator/sub-investigator.

For details, see the respective sections of the protocol.

- 1) Subjects who have signed the informed consent will undergo evaluation of DMARD response at the screening visit.
- 2) Follow-up will not be performed for subjects starting the extension study immediately after the Week 52 visit.
- 3) For details of the test parameters, refer to Section 5.4.4.
- 4) Subjects in the reference group will not undergo these procedures.
- 5) For pregnancy tests, serum samples will be used at the screening visit, and urine samples will be used at and after the baseline visit.
- 6) Central ECG should be performed on the same day as blood sampling for post-dose drug concentration at Week 4 or Week 8 before and after study drug administration.

- CONFIDENTIAL -

VI. ACCEPTABLE RANGE OF SCHEDULE OF ASSESSMENTS

The paragraphs that follow describe the allowable time windows on scheduled test and observation dates.

Reasonable efforts must be made to perform the tests and observations specified for early termination and follow-up, even if they cannot be conducted within the allowable time frame.

[Acceptable Time Ranges for Efficacy Tests]

TJC/SJC (68/66 joints) and CRP

Screening	From 1 to 28 days prior to the baseline visit.
Baseline	Before the initiation of treatment with the study drug or reference drug on the baseline visit day.

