Study visits from Week 4 to Week 48	Within ± 7 days of the protocol-specified date AND before the initiation of treatment with the study drug or reference drug on the visit day.
Week 52	Within ± 7 days of the protocol-specified date.
Early termination	Within 2 days of withdrawal.
Follow-up	Within ± 7 days of the date 28 days after the Week 52 OR early termination visit.

PGA (VAS), SGA (VAS), Subject's Assessment of Pain (VAS), HAQ-DI, and ESR

Baseline	Before the initiation of treatment with the study drug or reference drug on the baseline visit day.
Study visits from Week 4 to Week 48	Within ± 7 days of the protocol-specified date AND before the initiation of treatment with the study drug or reference drug on the visit day.
Week 52	Within ± 7 days of the protocol-specified date.
Early termination	Within 2 days of withdrawal.
Follow-up	Within ± 7 days of the date 28 days after the Week 52 OR early termination visit.

- CONFIDENTIAL -

SF-36 v2[®], WPAI

Baseline	Before the initiation of treatment with the study drug or reference drug on the baseline visit day.
Weeks 4, 8, 12, and 28	Within \pm 7 days of the protocol-specified date AND before the initiation of treatment with the study drug or reference drug on the visit day.
Week 52	Within \pm 7 days of the protocol-specified date.
Early termination	Within 2 days of withdrawal.
Follow-up	Within \pm 7 days of the date 28 days after the Week 52 OR early termination visit.

[Acceptable Time Ranges for Safety Tests]

Physical Examination, Vital Signs, Laboratory Tests [Hematology, Serum Biochemistry, Urinalysis, Pregnancy Test (serum/urine)]

Screening	From 1 to 28 days prior to the baseline visit.
Baseline	Before the initiation of treatment with the study drug or reference drug on the baseline visit day.
Study visits from Week 4 to Week 48	Within \pm 7 days of the protocol-specified date AND before the initiation of treatment with the study drug or reference drug on the visit day.
Week 52	Within \pm 7 days of the protocol-specified date.
Early termination	Within 2 days of withdrawal.
Follow-up	Within \pm 7 days of the date 28 days after the Week 52 OR early termination visit.

Body Weight

Screening	From 1 to 28 days prior to the baseline visit.
Weeks 12, 28, and 40	Within \pm 7 days of the protocol-specified date AND before the initiation of treatment with the study drug or reference drug on the visit day.
Week 52	Within \pm 7 days of the protocol-specified date.

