1.2.3 Toxicology

Nonclinical repeated-dose toxicity studies of ASP015K were conducted using rats (up to 26 weeks) and monkeys (up to 52 weeks). Toxicities observed in these studies were mainly related to gastrointestinal, hematopoietic, muscular, and immune systems. All these findings were reversible and resolved upon the withdrawal of ASP015K. Muscle toxicity was observed in monkeys: mild multifocal muscle necrosis in 1 female at 60 mg/kg/day in the 4-week preliminary study; elevation of CPK and LDH without histopathological changes in 2 males at 60 mg/kg/day in the 4-week preliminary study; elevation of CPK and LDH without histopathological changes in 1 male that was sacrificed in extremis in 13-week study, and a transient increase of CPK without histopathological changes observed in another male in the same 13-week study.

Genotoxicity studies were conducted *in vitro* and *in vivo*. ASP015K was negative in the reverse mutation test in bacteria but was positive in an *in vitro* chromosomal aberration test in Chinese hamster lung cells. ASP015K was negative in 2 *in vivo* genotoxicity studies, the unscheduled DNA synthesis test in rats and the micronucleus test in mice. These results suggested that ASP015K had little potential to induce chromosomal aberrations *in vivo*.

In toxicity studies on the fertility and early embryonic development in rats, the viability of embryos decreased after implantation and the number of live embryos decreased in the 100 mg/kg/day group compared with the control group. ASP015K neither induced general toxicity nor impacted male or female fertility up to the dose of 100 mg/kg/day. In an embryo–fetal development study in rats, increased incidences of skeletal abnormalities and variations and visceral variations were noted at 30 mg/kg/day and higher, while increased incidences of visceral and external abnormalities were observed at 300 mg/kg/day. NOAEL for embryo–fetal development in rats was 10 mg/kg/day. In an embryo–fetal developmental toxicity study in rabbits, no teratogenicity was observed; however, increased postimplantation loss and decreased numbers of live fetuses were noted at 10 mg/kg/day.

Four- and 13-week toxicity studies of ASP015K administered in combination with tacrolimus, MMF, or MTX demonstrated no significant synergistic toxicities.

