5.4.3 Adverse Events

The survey period for AEs will be from the initiation of treatment with the study drug or reference drug to before the initiation of administration in the extension study or until the end of follow-up.

Events that occurred after treatment with the study drug or reference drug until before the initiation of administration in the extension study or until the end of follow-up will be recorded as AEs. Concurrent diseases that worsened during the study will also be recorded as AEs. AEs that occurred after the subject has completed the study plan or has been discharged from the hospital or the study center will not be recorded.

AEs that have not resolved before the initiation of administration in the extension study or at the end of follow-up must be followed-up until resolved or judged to be no longer clinically significant or until they become chronic to the extent that they can be fully characterized. If the event resolves during the study period, the date of resolution is to be entered in the eCRF.

See Appendix 4 “Liver Safety Monitoring and Assessment” for the assessment of AEs caused by DILI.

Herpes zoster should be entered as an AE information in the eCRF, and also, a separate Herpes Zoster (shingles) Worksheet should be prepared, and a copy should be submitted to the sponsor. If the sponsor considers necessary and requests for submission of forms for the purpose of providing additional information on other AEs, a form must be prepared to report to the sponsor.

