5.5.7 Procedure in Case of Pregnancy

If a woman is proven to be pregnant during treatment with the study drug or reference drug or within 28 days from the end of treatment or early termination, the investigator should report this information to the sponsor/CRO in the same manner as that for an SAE. The expected date of delivery, last menstruation, estimated fertility date, pregnancy result and neonatal data etc., should be included in this information.

The investigator or other responsible personnel will handle the pregnancy in the same manner as an SAE and will follow the medical status of the mother, as well as the fetus, and report the outcome to the sponsor.

When the outcome of the pregnancy falls under the criteria for SAEs [spontaneous abortion, induced abortion, stillbirth, death of newborn, congenital anomaly (including anomaly in a miscarried fetus)] and when information on newborn falls under the criteria for SAEs (including death, congenital anomaly, and other anomalies), the investigator should respond in accordance with the report procedure for SAEs.

- CONFIDENTIAL -

Additional information regarding the outcome of a pregnancy (which is categorized as an SAE) is mentioned below.

“Spontaneous abortion” includes abortion and missed abortion.

Death of a newborn within 1 month after birth should be reported as an SAE regardless of its relationship with the study drug.

If a newborn dies more than 1 month after the birth, it should be reported if a relationship between the death and intrauterine exposure to the study drug is judged as “possible” by the investigator or other responsible personnel.

In the case of a delivery of a living newborn, the “normality” of the newborn is evaluated at the birth.

“Normality” of the miscarried fetus is evaluated by visual examination unless test results which indicate a congenital anomaly are obtained prior to miscarriage.

If a male subject impregnates his partner during the conduct of the clinical study, the subject should report the pregnancy to the investigator or other responsible personnel, and the investigator must report the pregnancy to the sponsor/CRO.

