7.9.1 Handling of Schedule of Assessments of Efficacy Variables

For data after the end of study treatment, data obtained within + 2 days after the last dose is taken will be included in analysis. For data after the end of reference treatment, data obtained within + 9 days after the last dose will be included in analysis.

- CONFIDENTIAL -

(1) TJC (68 joints)/SJC (66 joints), laboratory test (CRP)

Time points defined in analysis	Reference date*	Acceptable time range
Screening	Day -28 to Day -1	Day -28 to Day -1
Baseline	Day 1	Day 1
Week 4 to Week 48**	Day $7 \times x + 1$	Day $(7 \times x - 6)$ to Day $(7 \times x + 8)$ and before the initiation of treatment with the study drug or reference drug on the visit day
Week 52	Day 365	Day 358 to Day 372
End of Week 12 (Week 12 or at early termination before Week 12)	Day 85	Day 2 to Day 92
End of treatment (Week 52 or at early termination)	Day 365	Day 2 to Day 372

*: Day 1 represents the first day of study or reference treatment. The day before the initiation of treatment with the study drug or reference drug is expressed as Day -1.

** : Represents the reference date and acceptable time range for Week x.

(2) PGA and SGA (VAS), subject's assessment of pain (VAS), HAQ-DI, laboratory test (ESR)

Time points defined in analysis	Reference date*	Acceptable time range
Baseline	Day 1	Day 1
Week 4 to Week 48**	Day $7 \times x + 1$	Day $(7 \times x - 6)$ to Day $(7 \times x + 8)$ and before the initiation of treatment with the study drug or reference drug on the visit day
Week 52	Day 365	Day 358 to Day 372
End of Week 12 (Week 12 or at early termination before Week 12)	Day 85	Day 2 to Day 92
End of treatment (Week 52 or at early termination)	Day 365	Day 2 to Day 372

*: Day 1 represents the first day of study or reference treatment. The day before the initiation of treatment with the study drug or reference drug is expressed as Day -1.

** : Represents the reference date and acceptable time range for Week x.

(3) SF-36 v2[®], WPAI

Time points defined in analysis	Reference date*	Acceptable time range
Baseline	Day 1	Day 1
Week 4 to Week 28**	Day $7 \times x + 1$	Day $(7 \times x - 6)$ to Day $(7 \times x + 8)$ and before the initiation of treatment with the study drug or reference drug on the visit day
Week 52	Day 365	Day 358 to Day 372
End of Week 12 (Week 12 or at early termination before Week 12)	Day 85	Day 2 to Day 92
End of treatment (Week 52 or at early termination)	Day 365	Day 2 to Day 372

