Pregnancy testing	Screening, Baseline, Week 4, Week 8, Week 12, Week 16, Week 20, Week 24, Week 28, Week 32, Week 36, Week 40, Week 44, Week 48, Week 52, at early termination, follow-up, unscheduled	Serum pregnancy test (Included among biochemistry tests) Urine pregnancy test (In-hospital testing)	Human chorionic gonadotropin (hCG)
Acute phase reactants	Screening (CRP only), Baseline, Week 4, Week 8, Week 12, Week 16, Week 20, Week 24, Week 28, Week 32, Week 36, Week 40, Week 44, Week 48, Week 52, at early termination, follow-up, unscheduled	(Included among biochemistry tests)	CRP
		In-hospital testing	ESR
PK (Assessment of trough concentration)	Baseline, Week 4, Week 8, Week 12, Week 28, Week 52, at early termination	2 mL vacutainer tubes containing EDTA-3K	Concentrations of ASP015K and its metabolites H1, H2, and H4
Additional PK (for post-dose concentration)	Week 4 or Week 8	2 mL vacutainer tubes containing EDTA-3K	Concentrations of ASP015K and its metabolites H1, H2, and H4
PD	Baseline, Week 4, Week 8, Week 12, Week 28, Week 52, at early termination, follow-up, unscheduled	2 mL vacutainer tubes containing EDTA-2Na (MMP-3 is included among biochemistry tests.)	VEGF MMP-3
	Baseline, Week 4, Week 8, Week 12, Week 28, Week 52, at early termination, follow-up, unscheduled	2 mL vacutainer tubes containing EDTA-2K	Lymphocyte subset
Pharmacogenomics (Only at approved study centers)	After obtaining the subject's consent for PGx	5 mL vacutainer tubes containing EDTA-2K	PGx analysis

*: Types of collecting tube used at Korea and Taiwan are described in the laboratory handling manual.

- CONFIDENTIAL -

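### Read literally, Protocol 5.5.7 ends the duty to report a woman's pregnancy 28 days after treatment, but the scheduled follow-up pregnancy test may fall as late as day 35

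*Protocol*

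**What the plan says.** - **Reporting duty.** Protocol 5.5.7 applies when a woman is proven pregnant on treatment or "within 28 days from the end of treatment or early termination". The investigator then reports as for an SAE, supplies dating and outcome information, and follows mother and fetus. The sentence on male subjects' partners carries no day limit; it covers the conduct of the study.
- **Follow-up test.** Table 1 places the follow-up visit "28 days after Week 52 or early termination visit" and marks the pregnancy test there as mandatory. Appendix 2 lists pregnancy testing at visits ending with "Week 52, at early termination, follow-up, unscheduled". Section 5.4.4 exempts women in whom pregnancy can clearly be ruled out, such as postmenopausal women.
- **Test window.** Section VI includes the pregnancy test among the assessments allowed at follow-up within plus or minus "7 days of the date 28 days after the Week 52 OR early termination visit". It also asks for reasonable efforts to complete the assessments "specified for early termination and follow-up, even if they cannot be conducted within the allowable time frame".
- **Related periods.** The Definition of Key Study Terms sets the follow-up period at a nominal 4 weeks. Under 5.4.3, events "until the end of follow-up will be recorded as AEs". Under 5.1.6, women of childbearing potential use contraception for 60 days after treatment.

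**The concern.** The reporting limit sits at the centre of the test window, so a test done on time by the protocol's own schedule can fall after the reporting duty has lapsed. For women who do not go straight into the extension study, the follow-up test is the last scheduled chance to find a conception too recent to show at Week 52 or early termination.

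Section 5.5.7 is the only text that triggers follow-up of mother, fetus and outcome, and the sponsor would want that information for an exposed pregnancy. In rats given ASP015K, "increased incidences of skeletal abnormalities and variations and visceral variations were noted at 30 mg/kg/day and higher" (Protocol 1.2.3). In rabbits, postimplantation loss increased at 10 mg/kg/day.

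**Working it through.** The documents give no figure to reproduce. The check is a day count.

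**Inputs.** Reporting limit: 28 days (5.5.7). Follow-up test: 28 ± 7 days after the Week 52 or early termination visit (Section VI). Early termination is dated from the investigator's decision to discontinue (3.4), and the visit follows within 2 days of withdrawal (Section VI). The last etanercept dose is at Week 51 (5.1.1).

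**Formula.** Counted from the visit, permitted test days run from 28 − 7 = 21 to 28 + 7 = 35, which is 35 − 21 + 1 = 15 days. If the reporting clock starts *k* days before the visit, those 15 days become days 21 + *k* to 35 + *k*. The number beyond day 28 is then (35 + *k*) − 28 = 7 + *k*.

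| Reporting clock starts at | *k* | Test days on that clock | On-target test | Permitted days beyond 28 |
|---|---|---|---|---|
| Week 52 or early termination visit | 0 | 21–35 | 28 | 7 of 15 (46.7%) |
| Last oral dose, assumed the day before Week 52 | 1 | 22–36 | 29 | 8 of 15 |
| Decision to discontinue, assumed to be the withdrawal date, with the visit 2 days later | 2 | 23–37 | 30 | 9 of 15 |
| Last etanercept dose, 365 − (1 + 7 × 51) = 365 − 358 | 7 | 28–42 | 35 | 14 of 15 |

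**Check in study days, Week 52 visit on Day 365.** The limit is 365 + 28 = Day 393. The window is Days 386 to 400, so Days 394 to 400 (7 days) lie outside. For etanercept the limit is 358 + 28 = Day 386, so Days 387 to 400 (14 days) lie outside. A visit done late under the reasonable-efforts rule adds to any of these counts.

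**Whether another rule supplies the duty.**
- Protocol 5.4.4 says what a positive urine test means for staying in the study. It states no reporting duty and excludes pregnancy testing from the safety assessment.
- Appendix 3 does not list pregnancy among events always considered serious, although it does list congenital anomalies.
- Protocol 5.5.6 and the later paragraphs of 5.5.7 bring in serious outcomes such as abortion, stillbirth and congenital anomaly, but not the pregnancy itself.
- SAP 7.5.6 only lists pregnancies.

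None requires a pregnancy first proven on days 29 to 35 to be reported or followed.

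**The case against.** The strongest objection concerns grammar. The time phrase in 5.5.7 can attach to being pregnant rather than to the date of proof. The same paragraph asks for last menstruation and an estimated date of conception, which date the pregnancy and not the test. On that reading, a day-33 test that reveals an on-treatment conception is reportable. A reader might infer that on-treatment conceptions are shut out whenever the test is late, but the wording does not establish that. The objection stands in part: it lowers confidence, but it leaves the duty dependent on a generous reading.

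A reader might also infer that the protocol contradicts itself by recording an AE at a day-33 visit while ignoring a pregnancy found at the same visit. The nominal 4-week follow-up definition does not support stating this as settled. Four weeks is 28 days, so the two periods end together unless follow-up is taken to last until the actual visit.

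Nor does 46.7% mean that nearly half of pregnancies would be missed. It is a share of permitted days from one starting point. Nothing suggests visits spread evenly over the window, and the on-target day is inside the limit when counted from the visit.

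Several facts keep the matter small, and they stand. Exclusion criteria 26 and 27 make pregnancy unlikely. Tests run every 4 weeks through Week 52, some women are exempt, and those who start the extension immediately after Week 52 have no follow-up visit.

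**Conclusion.** The mismatch is in the text. If the 28 days limit the date of proof, 7 of the 15 permitted test days carry no literal duty when counted from the Week 52 or early termination visit. Up to 14 of 15 do so on the last-etanercept-dose count. The documents do not say which starting point governs 5.5.7, so none of these counts is definitive.

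The number of pregnancies affected cannot be estimated from the documents and should be very small. What can escape is mainly a conception too recent to show at Week 52 or early termination, or a later one. Sample size, type I error and the primary analysis are unaffected. This is a cheap improvement at moderate confidence, not a demonstrated error.

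**What to change.** In the first sentence of 5.5.7, make a woman's pregnancy reportable if it is proven (a) during treatment, (b) within 28 days from the end of treatment or early termination, or (c) by any protocol-required test up to and including the follow-up visit, whatever its day. Part (c) brings the uncovered permitted days to 0 of 15 on every count above and also covers late visits. The partner sentence can stay as it is.

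The cost is one sentence of protocol text and a few more site reports, with no added visits or tests.

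Extending the limit to 60 days is optional. It would match the contraception period for women and leave 60 − 35 = 25 days to spare counted from the visit, or 60 − 42 = 18 counted from the last etanercept dose. It is not needed to close the gap, the documents do not require the two periods to be equal, and capture after the follow-up visit would be passive because no later contact is scheduled.
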